4.2. Inclusion Criteria

Only individuals who meet all of the following criteria may be enrolled in the study.

1. Must have successfully completed Study KZR-616-003 through Week 32, including the Week 32 Visit assessments, be willing and able to provide written informed consent prior to any study-related procedures, and be willing and able to comply with study requirements.
2. Women of childbearing potential (WOCBP) must have a negative urine or serum pregnancy test prior to the first dose of KZR-616 in KZR-616-003E, and must agree to continue to use a highly effective method of birth control until completion of the study (or 30 days following the last dose of KZR-616 in case of early withdrawal). Women of childbearing potential are defined as postpubescent female patients, unless the patient is postmenopausal (defined by amenorrhea for at least 2 years or amenorrhea for at least 1 year with confirmatory follicle stimulating hormone [FSH] level in the postmenopausal range, as documented historically or measured by the central or local laboratory and if patient is not on supplementary hormonal therapy) or surgically sterile (ie, tubal ligation, hysterectomy, bilateral salpingoophorectomy). See [Section 7.2.8](#) for detailed requirements for WOCBP.
3. Male patients must continue to use an effective contraception method (eg, condom with spermicide) for 1 week following their last dose of KZR-616 or be congenitally or surgically sterile (eg, vasectomy with documented confirmation of post-surgical aspermia).

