4.3. Exclusion Criteria

Only individuals who do not meet any of the following criteria may be enrolled in the study.

1. Have clinical evidence of significant unstable or uncontrolled diseases other than the disease under study (eg, cardiac [including congestive heart failure, hypertension, angina,

or myocardial infarction], pulmonary [including pulmonary hypertension or interstitial lung disease], hematologic, gastrointestinal, endocrinologic, hepatic, renal, neurological, or infectious disease, any ongoing SAE(s), or AE(s) \geq Grade 3 by National Cancer Institute Common Terminology Criteria for Adverse Events [NCI-CTCAE]) that, in the opinion of the Investigator or Sponsor/designee, could confound the results of the study, put the patient at undue risk, or interfere with protocol adherence.

2. Has participated in any clinical study other than KZR-616-003 between the Week 32 Visit of Study KZR-616-003 and the first study visit of KZR-616-003E, if they are not on the same calendar day.
3. Are females who are breastfeeding or who plan to become pregnant during the study, or who are actively trying to conceive at the time of signing of the informed consent form (ICF).
4. Have hypersensitivity to KZR-616 or any of its excipients.

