6. DOSAGE AND KZR-616 ADMINISTRATION

6.1. KZR-616 Administration

KZR-616 will be administered by SC injection once weekly. The first injection will be a 30-mg dose, administered at the study site, and subsequent injections will be a 45-mg dose. Ideally, the first dose will be given on the same calendar day as the Week 32 Visit of Study KZR-616-003, but must be given no later than 8 weeks after the Week 32 Visit of Study KZR-616-003.

After the first dose, KZR-616 will be administered by study personnel at the site or by a home health provider at the patient's home. At-home administration of KZR-616 by the patient or caregiver may also be available as an option, as appropriate (see [Section 5.4](#)). Doses will be administered according to the Schedules of Assessments ([Table 1](#) and [Table 2](#)).

Further details regarding drug product formulation, preparation, and administration of KZR-616 will be provided in a separate Pharmacy Manual.

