Adverse events	← →										

Abbreviations: CDASI=Cutaneous Dermatomyositis Disease Area and Severity Index; CRP=C-reactive protein; DM=dermatomyositis; DNA=deoxyribonucleic acid; ECG=electrocardiogram; EOS=End of Study; EOT=End of Treatment; EQ-5D-5L=EuroQoL 5-dimension 5-level; ETV=Early Termination Visit; FI-2=Functional Index-2; HAQ-DI=Health Assessment Questionnaire-Disability Index; hCG=beta-human chorionic gonadotropin; IgG=immunoglobulin G; MDAAT=Myositis Disease Activity Assessment Tool; MDI=Myositis Damage Index; MDGIC=Physician Global Impression of Change; MMT-8=Manual Muscle Testing-8 Muscle Groups; NRS=numerical rating scale; PD=pharmacodynamics; PROM=patient-reported outcome measure; PtGADA=Patient Global Assessment of Disease Activity; PtGADD=Patient Global Assessment of Disease Damage; PGIC=Patient Global Impression of Change; RNA=ribonucleic acid

a Patients will be evaluated for eligibility at, or within 8 weeks after, the Week 32 Visit of Study KZR-616-003. Informed consent must be signed prior to any study-related activity in KZR-616-003E. The KZR-616-003 Week 32 Visit may also serve as Visit 1 (Day 1) for the open-label extension study. Assessments at this visit performed as part of Study KZR-616-003 will be used as baseline values for the extension study; therefore, these assessments must be performed prior to the first dose of open-label KZR-616.

b Patients who provide additional informed consent will undergo blood sampling for genetic analysis.

c Eligibility criteria for this study should be assessed only after the Week 32 assessments for Study KZR-616-003 have been completed and informed consent for Study KZR-616-003E has been signed. All data except central laboratory results from samples drawn at that visit should be used to confirm patient eligibility.

d Data from Study KZR-616-003 will be used.

e Women of childbearing potential only. Positive urine pregnancy tests will be confirmed with a serum hCG test.

f Assessments done as part of the Week 32 Visit of Study KZR-616-003.

g Vital signs will be collected prior to dosing. Blood pressure and pulse rate should be collected after the patient has been resting for at least 5 minutes in the seated position. If the blood pressure is elevated on the first measurement at Screening/Baseline, it should be repeated after at least an additional 5 minutes of rest. It is recommended that blood pressure be measured using the same arm at each assessment.

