7.2.8. Contraception Requirements and Pregnancy Testing

Women of childbearing potential must have a negative urine pregnancy test before doses of KZR-616 outlined in [Table 1](#) and [Table 2](#), and must agree to use highly effective and medically acceptable methods of contraception to prevent pregnancy during the study and for 4 weeks after administration of the last dose of KZR-616. For the purposes of this study, WOCBP are defined as postpubescent female patients, unless the patient is postmenopausal (defined by amenorrhea for at least 2 years or amenorrhea for at least 1 year with confirmatory FSH level in the postmenopausal range, as documented historically or measured by the central or local laboratory and if patient is not on supplementary hormonal therapy) or surgically sterile (ie, tubal ligation, hysterectomy, bilateral salpingoophorectomy).

Highly effective contraception is defined as the use of an intrauterine device or hormonal contraceptives (eg, implant or oral) or having a vasectomized partner. In regions where it is considered highly effective contraception, 2 barrier methods (eg, female diaphragm and male condom OR 1 barrier method with spermicide) may be used.

If using a hormonal form of contraception, use must have been stable for at least 4 weeks prior to the Week 1 Day 1 Visit, and if using concomitant mycophenolate, the patient must use another highly effective nonhormonal form of contraception. Abstinence will be acceptable only if it is in line with the preferred and usual lifestyle of the patient. Periodic abstinence (eg, calendar, ovulation) and withdrawal are not acceptable methods of contraception.

For WOCBP, urine pregnancy testing will be performed at the time points shown in [Table 1](#) and [Table 2](#). KZR-616 should not be administered prior to confirmation of a negative test at visits at which pregnancy tests are performed. Positive urine pregnancy tests should be confirmed by a serum pregnancy test.

Samples for FSH testing may be collected at any time during the study to confirm postmenopausal status in female patients whose childbearing potential status has changed since the Screening Visit of Study KZR-616-003. Only after confirmation of postmenopausal status is pregnancy testing not required.

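### Table 1 leaves Week 32 central laboratory results out of eligibility, and sources Visit 1 safety assessments from Week 32, without a clear rule for a first dose up to 8 weeks later

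*Combined protocol and SAP*

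**What the plan says.** Section 6.1 states a preference and a limit for the first open-label dose. The preference is same-day rollover: "Ideally, the first dose will be given on the same calendar day as the Week 32 Visit of Study KZR-616-003". The limit is that it "must be given no later than 8 weeks after the Week 32 Visit of Study KZR-616-003". Sections 3.1 and 4.1 give the same 8-week window for evaluating eligibility. Exclusion 2 in Section 4.3 also allows for a first extension visit on a different date from Week 32.

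The Table 1 footnotes do not set out separate rules for the two cases:

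- Footnote c, on eligibility: "All data except central laboratory results from samples drawn at that visit should be used to confirm patient eligibility".
- Footnote f marks the Visit 1 entries for the pregnancy test, physical examination, vital signs, weight, ECG, and hematology and chemistry: "Assessments done as part of the Week 32 Visit of Study KZR-616-003".
- Footnote a says the Week 32 Visit may double as Visit 1 and takes its values as the extension baseline. Its only timing condition is that they come before the first dose.
- Footnote g has vital signs taken before dosing.

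Three other provisions bear on the same visit:

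- Exclusion 1 (Section 4.3) begins "Have clinical evidence of significant unstable or uncontrolled diseases other than the disease under study". It names hematologic, hepatic and renal disease and adverse events of Grade 3 or higher, subject to the opinion of the investigator or sponsor.
- Inclusion 2 (Section 4.2) says women of childbearing potential "must have a negative urine or serum pregnancy test prior to the first dose of KZR-616 in KZR-616-003E". It sets no maximum age for that test.
- Section 7.2.8 adds: "KZR-616 should not be administered prior to confirmation of a negative test at visits at which pregnancy tests are performed".

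**The concern.** Leaving pending central results out of the eligibility check is sensible when the patient is dosed on the day the blood is drawn. That reason lapses once the laboratory has reported. Footnote c carries no timing condition, so for a patient first dosed weeks later it still omits the most recent scheduled central results. Those results bear directly on conditions that exclusion 1 asks the site to consider.

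Footnote f raises a related problem. Taken literally, it lets a Week 32 pregnancy test, examination, vital signs, ECG and laboratory panel stand for Visit 1 when Visit 1 is up to 56 days later. Section 7.2.8 and footnote g can be read the other way, so two sites could follow different procedures and each cite the protocol.

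At stake are a safety check at the start of weekly dosing and the meaning of the safety baseline. Section 10 summarizes laboratory and vital-sign change from baseline. Where Week 32 is that baseline, the change includes the interval before dosing as well as time on treatment.

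**Working it through.** **Inputs.** Maximum gap from Week 32 to first dose: 8 weeks (Section 6.1). First on-treatment laboratory draw: Day 78 ± 14 (Table 1). First on-treatment pregnancy test and vital signs: Day 22 ± 1, then Day 50 ± 1 (Table 2), then Day 78 ± 14 (Table 1). Doses are weekly from Day 1. Central laboratory turnaround is not stated, so I assume 1 to 21 days.

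**Maximum age of Week 32 assessments at first dose.** 8 × 7 = 56 days; 0 days with same-day rollover.

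**Laboratory interval.** Day 78 is 78 − 1 = 77 days after Day 1.

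- Same-day rollover: 77 days nominal; 77 − 14 = 63 to 77 + 14 = 91.
- 8-week gap: 56 + 77 = 133 days nominal; 133 − 14 = 119 to 133 + 14 = 147.
- Nominal doses before that draw: Days 1, 8, …, 71, which is 11 in either case.

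**Pregnancy-test and vital-sign interval.** Day 22 is 21 days after Day 1.

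- Same-day rollover: 21 days (± 1).
- 8-week gap, if nothing is repeated at Visit 1: 56 + 21 = 77 days (± 1).
- Doses before Day 22: Days 1, 8 and 15, which is 3 in either case.
- For comparison, the next nominal intervals are 50 − 22 = 28 and 78 − 50 = 28 days.

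**Would Week 32 results be in hand at the first dose?** With turnaround t days, the share of the 56-day window that falls after reporting is (56 − t)/56:

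| Assumed t (days) | Share of window |
|---|---|
| 1 | 55/56 = 98% |
| 7 | 49/56 = 88% |
| 14 | 42/56 = 75% |
| 21 | 35/56 = 63% |

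These are shares of the permitted window, not of patients. Same-day dosing is preferred, so first doses may cluster at day 0, where the exception is reasonable.

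**The passages for a Day 1 later than Week 32.**

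- Footnote f, read alone: the Visit 1 pregnancy test and vital signs are those of Week 32.
- Footnote a: can be read as covering only the case where Week 32 doubles as Visit 1, or as fixing the baseline whatever the gap.
- Section 7.2.8 and footnote g: a negative test and vital signs before a dose. Table 1 lists a test, vital signs and a dose at Visit 1, but the test and vital-sign entries carry footnote f.
- Inclusion 2: any earlier negative test satisfies its wording.

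No provision says which reading governs.

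**The case against.** The strongest reply is that footnote c lists what eligibility should rest on and does not tell anyone to disregard a reported abnormality. A reader might infer that the protocol obliges sites to dose despite a known abnormal result. The documents do not support that:

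- Exclusion 1 turns on investigator or sponsor opinion and sets no laboratory threshold.
- An abnormal laboratory finding can be an adverse event (Section 9.1.1), and adverse events are collected from consent (Section 9.1.5).
- Clinically significant results should be repeated (Section 7.2.6.4). A repeat sample is not a Week 32 sample, so footnote c does not omit it.
- Unscheduled visits may include any Week 24 procedure (Section 7.1.1).
- An event judged to contraindicate dosing stops it (Section 8.1.2).

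These protections are real but partial. They rely on someone acting on the result; none makes the Week 32 laboratory results part of the eligibility check or limits the age of the pregnancy test.

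A reader might also infer that no Visit 1 pregnancy test or vital signs are needed after a gap. Section 7.2.8, footnote g and the same-day reading of footnote a leave that open. What stands is an ambiguity.

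A third tempting inference is that changes during the gap will be attributed to KZR-616. The study is descriptive, Section 10 leaves details to a later SAP, and Groups 1 and 2 are summarized from the first KZR-616 dose in the parent study, so Week 32 need not be the reference there. Only the conditional statement holds: where Week 32 is the baseline, change from baseline includes the gap.

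Finally, the 133 (119 to 147) days apply to laboratory tests only, since vital signs and pregnancy tests recur from Day 22. Of the 133 days, 77 are the plan's ordinary interval. Figure 1 is not shown and parent-study follow-up after Week 32 is not described, so other safeguards may exist.

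**Conclusion.** The point holds as a defect of wording with a modest safety consequence. Footnote c omits Week 32 central results whatever the gap, which sits poorly with exclusion 1 once those results are reported. That they would usually be reported before a delayed first dose is an inference from an assumed turnaround; it does not hold for a dose within a few days of Week 32. Footnote f is in tension with footnote g and Section 7.2.8 for a separate Day 1, and inclusion 2 does not settle the matter.

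At the limit, Visit 1 assessments are 56 days old at first dose, and the scheduled laboratory interval rises from 77 to 133 days. How many of the up to 24 patients have any gap is unknown, so the figures describe what the plan permits rather than what will be typical. It should be corrected because sites can act on it and the change is small.

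**What to change.** 1. **Footnote c.** Limit the exception to central results not yet available at the first dose, and reconcile the footnote with exclusion 1. This uses results already in hand and needs no new procedure.
2. **Footnotes a and f.** Reconcile them with footnote g, inclusion 2 and Section 7.2.8 for a Day 1 later than the Week 32 date. The sponsor's clinical team should state which Visit 1 assessments apply in that case and which values serve as the safety baseline. Those are clinical decisions, and this review does not propose them.
3. **SAP.** Carry the chosen safety baseline into the SAP. Where it is Week 32, note that change from baseline includes any gap before dosing.

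The cost is a few footnote edits and a sentence in the SAP. If the clinical team decides that anything is to be repeated, it concerns only patients with a gap, and Section 6.1 already places the first dose at the study site.

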7.2. Study Procedures and Assessments

All patients must be provided a consent form describing the study with sufficient information for them to make an informed decision regarding their participation as per [Section 11.3](#). Informed consent must be signed prior to any procedures for the open-label extension. All study procedures and assessments should be performed according to the schedules presented in [Table 1](#) and [Table 2](#).

If a patient is not able to come to the study site for an on-site visit as per the Schedule of Assessments ([Table 1](#)), a telehealth visit should occur. Please refer to [Sections 7.2.4](#), [7.2.6.1](#), [7.2.6.2](#), and [7.2.6.3](#) for additional information regarding assessments performed at telehealth visits.

7.2.1. Demographic Data

Demographic data collected in KZR-616-003 will be used for this study.

7.2.2. Polymyositis/Dermatomyositis Classification

Patient classification of PM or DM based on the 2017 ACR/European League Against Rheumatism (EULAR) classification criteria ([Lundberg 2016](#)) from KZR-616-003 will be used for this study.

7.2.3. Medical History

Medical history data collected in KZR-616-003 will be used for this study, with the potential to update.

7.2.4. Efficacy Assessments

Efficacy assessments will be performed for all patients, unless indicated otherwise, at the visits shown in the Schedule of Assessments ([Table 1](#)). As interrater reliability may result in increased variability of within-patient assessments, it is recommended that the same individual performs the assessments at all visits for an individual patient. All personnel performing the assessments must be qualified to perform them.

Websites for the individual assessments (where available) are provided in [Section 13.2](#) (Appendix B).

7.2.4.1. Total Improvement Score (TIS)

The TIS uses the 6 IMACS core set measures, combining the absolute percentage change in each with varying weights to obtain a TIS on a scale of 0-100. Thresholds of improvement have been set for minimal, moderate, and major response. The TIS is the primary outcome measure for this study, and will not be calculated by sites.

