1.5. Rationale for Study Endpoints

The Myositis Response Criteria are recommended for use as primary endpoints in myositis therapeutic trials. The criteria use core set activity measures (CSAMs) from the International Myositis Assessment and Clinical Studies Group (IMACS). By combining the absolute percentage change in these 6 core set measures (each with varying weights), a Total Improvement Score (TIS), ranging from 0 to 100, is obtained. The IMACS CSAMs consist of:

- Manual Muscle Testing-8 Muscle Groups (MMT-8)
- Physician Global Assessment (MDGA)
- Patient Global Assessments of Disease Activity (PtGADA)
- Health Assessment Questionnaire-Disability Index (HAQ-DI)
- Muscle enzymes (clinical laboratory assessments): CK, aldolase, lactate dehydrogenase (LDH), alanine aminotransferase (ALT), and aspartate aminotransferase (AST)
- Myositis Disease Activity Assessment Tool (MDAAT, 2005 version)

In addition, IMACS has defined the following core set damage measures (CSDMs):

- Myositis Damage Index (MDI)
- Patient Global Assessment of Disease Damage (PtGADD)

Mean change from start to end of KZR-616 treatment was the primary efficacy endpoint for Study KZR-616-003, and secondary and exploratory endpoints utilized the CSAMs and CSDMs, along with other measures of function and outcomes. To determine long-term efficacy in the same patient population, many of the endpoints used in Study KZR-616-003 will also be used in this study with consideration for treatment periods (see [Section 10](#)).

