7.2.4.4. Physician Global Assessment of Disease Activity (MDGA)

This tool measures the global evaluation by the treating physician of the overall disease activity of the patient at the time of assessment using a 10 cm visual analog scale (VAS) and a 5-point Likert scale ([Rider 2011](#)).

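### Table 1 does not schedule the Physician Global Assessment (MDGA), one of the six measures needed to calculate the primary outcome measure, the TIS

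*Combined protocol and SAP*

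**What the plan says.** Section 7.2.4.1 defines the score: "The TIS uses the 6 IMACS core set measures, combining the absolute percentage change in each with varying weights". It then gives the score its role: "The TIS is the primary outcome measure for this study, and will not be calculated by sites". Section 1.5 lists the six measures: MMT-8, MDGA, PtGADA, HAQ-DI, muscle enzymes and MDAAT.

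Section 7.2.4.4 describes the MDGA separately: "This tool measures the global evaluation by the treating physician of the overall disease activity of the patient at the time of assessment". It is recorded on a 10 cm visual analogue scale and a 5-point Likert scale. The section names no visits.

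Timing comes from the schedules. Section 7.2.4 states: "Efficacy assessments will be performed for all patients, unless indicated otherwise, at the visits shown in the Schedule of Assessments". Section 7.2 says the same of procedures in general: "All study procedures and assessments should be performed according to the schedules presented in" Tables 1 and 2.

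The physician-rating row of Table 1 names the MDAAT and the MDGIC only. This part of the abbreviation list under the table shows the neighbouring terms, without the MDGA: "MDAAT=Myositis Disease Activity Assessment Tool; MDI=Myositis Damage Index; MDGIC=Physician Global Impression of Change; MMT-8=Manual Muscle Testing-8 Muscle Groups". Table 2 covers vital signs, pregnancy tests and dosing.

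**The concern.** The protocol needs the MDGA for its main efficacy measure but never tells sites when to record it. The omission is easy to miss because the MDGIC, whose abbreviation is similar, sits in the row where the MDGA would be expected.

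Four listed endpoints draw on the MDGA, through the TIS or through the list of core set activity measures:

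- mean change in TIS (Section 2.2.1);
- the TIS response categories at 20, 40 and 60 (Section 2.2.1);
- the individual core set activity measures (Section 2.2.1), for the MDGA part;
- corticosteroid-free TIS response (Section 2.2.3).

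The IMACS definition of improvement may be a fifth, but the protocol does not state its components.

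The rating describes disease activity at the moment of assessment, so a missed value cannot be recovered later. The written queries for missing data in Section 11.10 help only if the eCRF has a field for the MDGA. Early termination visits follow Table 1 (Section 8.4), and optional procedures at unscheduled visits come from the Week 24 list (Section 7.1.1), so both inherit the gap. The study is descriptive, so no hypothesis test is affected. What is at stake is whether the main efficacy measure can be calculated.

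**Working it through.** This is a count and a comparison of lists; no sample-size or power formula applies.

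**Step 1. Reproduce the plan's figure of six.** Section 1.5 lists six core set activity measures, which agrees with Section 7.2.4.1. Each is traced to Table 1:

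| Core set measure | Place in Table 1 |
|---|---|
| MMT-8 | own row |
| MDGA | none |
| PtGADA | row shared with HAQ-DI and PGIC |
| HAQ-DI | row shared with PtGADA and PGIC |
| Muscle enzymes | laboratory row, through Sections 7.2.6.4 and 7.2.6.5 |
| MDAAT | row shared with MDGIC |

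Scheduled: 6 − 1 = 5 of 6.

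**Step 2. Compare every described tool with the table.**

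- Sections 7.2.4.2 to 7.2.4.9 describe 8 tools: MMT-8, MDAAT, MDGA, MDGIC, FI-2, sit-to-stand, MDI and CDASI.
- Sections 7.2.5.1 to 7.2.5.6 describe 6: PtGADA, HAQ-DI, PGIC, EQ-5D-5L, PtGADD and Peak Pruritus NRS.
- Described: 8 + 6 = 14.
- With a Table 1 row: 7 + 6 = 13.
- Without one: 14 − 13 = 1, the MDGA.

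The TIS is left out of the count because it is a derived score that sites do not calculate.

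**Step 3. Count the visits affected.** The row for the MDAAT and MDGIC covers Visit 1, Weeks 12, 24, 36, 48, 60, 72, 84 and 96, and the End of Study visit: 1 + 8 + 1 = 10 time points, of which 8 + 1 = 9 are post-baseline. The other five components are also scheduled at all 10. As written, a complete six-measure set is scheduled at 0 of the 9 post-baseline visits. With the MDGA added to that row, it is scheduled at 9 of 9.

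**Step 4. Test whether another entry covers the MDGA.**

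- *MDAAT.* Section 7.2.4.3 describes it as organ-system scales (MYOACT) plus an intention-to-treat index (MITAX). No overall physician rating is named, and Section 1.5 counts the MDAAT and MDGA as separate measures.
- *MDGIC.* Section 7.2.4.5 describes a single 7-point item on change. The MDGA rates current activity.
- *An implied link, as for muscle enzymes.* The enzymes have no row under that name, but Section 7.2.6.5 refers to Section 7.2.6.4, which points to Table 1. Section 7.2.4.4 has no such link.

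**The case against.** The strongest reply is that the consequence is conditional. Section 3.1 says that safety and efficacy assessments take place at the on-site visits and refers to Section 7.2.4 for what they are; the MDGA is among them. Section 2.2.1 assumes that core set measures were ascertained at the start of KZR-616-003, and every patient comes from that study. Sites may already be recording the MDGA on the eCRF or with the MDAAT. The eCRF is not available here, so the documents cannot show that a single value would be lost. That much stands. It does not supply the missing entry, because Section 3.1 itself refers to Table 1 for what is done at each visit.

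A row could also have been lost when the table was converted to text. Several footnote markers in Table 1 are visibly damaged. The abbreviation list is only partial evidence against a lost row: it defines DNA and PD, which appear in no visible row, and it has no entry for the sit-to-stand test, which does have a row. The absence of the MDGA from Appendix B adds little, since that appendix lists websites only where available and omits four other tools. A lost row is therefore not excluded, although the absence of the MDGA from rows, footnotes and abbreviations alike makes it less likely.

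Finally, the study is small (up to 24 patients) and descriptive, and rules for missing data are left to the SAP. This limits the inferential harm but does not make the score calculable: Section 10 allows no imputation beyond what the SAP defines in advance.

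**Conclusion.** The concern holds. The protocol requires the MDGA for its primary outcome measure and omits it from the schedules that govern when assessments are done. As written, 5 of 6 TIS components and 13 of 14 described tools are scheduled, and four listed endpoints depend on the missing one.

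The omission in the supplied text is clear, subject to the small possibility of a conversion error. The loss of data is conditional: it assumes that sites and the eCRF follow Table 1 and that no other form captures the rating. The documents give neither the eCRF nor the component weights, so no patient-level loss and no effect on the score can be estimated. Because a missed rating cannot be reconstructed, the inconsistency must be corrected rather than left to site practice.

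**What to change.** Add the MDGA to the Table 1 row that now holds the MDAAT and MDGIC, at Visit 1, Weeks 12 to 96 (including the end-of-treatment and early termination visits) and End of Study. Add it to the abbreviation list.

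At Visit 1, use footnote f ("Assessments done as part of the Week 32 Visit of Study KZR-616-003") only if that visit did record the MDGA. Otherwise, collect it before the first open-label dose.

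If the MDGA is already captured on another form, say so in Section 7.2.4.4 and in a Table 1 footnote instead. In either case, confirm that the eCRF has the field.

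The cost is one short physician rating at each of 10 time points where physician ratings are already made, plus the eCRF check. The change to Table 1 is a protocol amendment and needs IRB/IEC approval under Section 11.2.

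Two matters remain outside this fix. The MMT-8 is not assessed at telehealth visits (Section 7.1.2), which is a separate limit that the protocol discloses. The rule for a TIS with a missing component still has to come from the SAP.
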